Table LAIH.2.	Schedule of Activities.....	13
Table LAIH.3.	Objectives and Endpoints.....	21
Table LAIH.4.	Treatment Regimens.....	32
Table LAIH.5.	Study Power Calculation.....	48
Table LAIH.6.	Populations for Analyses	49

List of Figures

Figure		Page
Figure LAIH.1.	Patient flow overview Clinical Protocol H8H-JE-LAIH.....	24
Figure LAIH.2.	Allowance of restricted rescue/ recurrence medications	34

List of Appendices

Appendix		Page
Appendix 1.	Abbreviations and Definitions.....	57
Appendix 2.	Clinical Laboratory Tests.....	60
Appendix 3.	Study Governance Considerations.....	61
Appendix 4.	Hepatic Monitoring Tests for Treatment-Emergent Abnormality.....	65
Appendix 5.	eDiary Assessments.....	66
Appendix 6.	Protocol Amendment H8H-JE-LAIH(a) Summary: Randomized, Double-blind, Placebo-controlled Trial of Lasmiditan in a Single Migraine Attack in Japanese Patients Suffering from Migraine With or Without Aura – the MONONOFU study.....	67

1. Synopsis

Title of Study:

Protocol H8H-JE-LAIH RandoMized, DQuble-bliNd, PlacebQ-coNtrolled Trial Of Lasmiditan in a Single Migraine Attack in Japanese patients SuFfering from Migraine With or WithoUt Aura – the MONONOFU sutdy

Rationale:

In 2 Phase 3, randomized, double-blind, single migraine attack studies (Study COL MIG-301/H8H-CD-LAHJ [Study 301/LAHJ, SAMURAI] and Study COL MIG-302/H8H-CD-LAHK [Study 302/LAHK, SPARTAN]), lasmiditan (Study 301/LAHJ: 100 mg and 200 mg, Study 302/LAHK: 50 mg, 100 mg, and 200 mg) demonstrated statistically significant superiority versus placebo in the proportion of patients who were headache pain free at 2 hours postdose as well as the proportion of patients who were free of their migraine-associated most bothersome symptom (MBS) (as identified by the patient from the associated symptoms of nausea, phonophobia or photophobia) at 2 hours postdose.

Lasmiditan in Japan is currently being developed for patients with migraine based on the bridging strategy described in the Guidance on Ethnic Factors in the Acceptability of Foreign Clinical Data (ICH-E5). Influences of ethnic factors on lasmiditan were evaluated in the Phase 1 Study H8H-JE-LAIE (Study LAIE), which explored the safety, tolerability and pharmacokinetics (PK) of lasmiditan in healthy Japanese and Caucasian subjects. The safety and PK results from this study, as well as the results from previous global clinical pharmacology studies, suggest that lasmiditan is unlikely to be affected by intrinsic ethnic factors and support the bridging strategy.

Study H8H-JE-LAIH (LAIH) will be conducted as the bridging trial to the Phase 3 Study 302/LAHK, with dose-response in efficacy of lasmiditan in the range of 50-200 mg. Study LAIH will assess the efficacy and safety of lasmiditan in acute treatment of a migraine attack in Japanese adult patients with or without aura.

Objectives/Endpoints:

Objectives	Endpoints
Primary	

 To evaluate the efficacy of lasmiditan 200 mg on migraine headache pain freedom compared to placebo 	
 The proportion of patients in each group who are pain free (defined as moderate or severe headache pain becoming none) at 2 hours postdose during the attack
Key Secondary	

 To evaluate the dose response of lasmiditan 200 mg, 100 mg, and 50 mg on migraine headache pain freedom compared to placebo 	
 The proportion of patients in each group who are pain free at 2 hours postdose during the attack

 To evaluate the efficacy of lasmiditan 100 mg on migraine headache pain relief compared to 	
 The proportion of patients with pain relief (defined as moderate or severe headache pain becoming mild or none) in each group at 2 hours postdose during the attack

placebo	
Other Secondary	

 To evaluate the efficacy of lasmiditan 100 mg and 50 mg on migraine headache pain freedom compared to placebo 	
 The proportion of patients in each group who are pain free at 2 hours postdose during the attack

 To evaluate the efficacy of lasmiditan 200 mg, 100 mg, and 50 mg on freedom from MBS compared to placebo 	
 The proportion of patients in each group who are free of MBS associated with migraine at 2 hours postdose during the attack

 To evaluate the efficacy of lasmiditan 200 mg, and 50 mg on pain relief compared to placebo 	
 The proportion of patients with pain relief in each group at 2 hours postdose during the attack

 To evaluate the efficacy of lasmiditan 200 mg, 100 mg, and 50 mg on sustained freedom from pain compared to placebo 	
 The proportion of patients in each group with 24-hour and 48-hour sustained pain freedom during the attack defined as pain free at 2 and 24 hours, and 2 and 48 hours, respectively, with no rescue medication

 To evaluate the efficacy of lasmiditan 200 mg, 100 mg, and 50 mg at 2 hours on freedom from symptoms associated with migraine compared to placebo 	
 The proportion of patients in each group that are free of symptoms associated with migraine at 2 hours postdose during the attack, including each of the following: phonophobia, photophobia, nausea, and vomiting

 To explore the time course of lasmiditan 200 mg, 100 mg, and 50 mg efficacy compared to placebo 	
 The proportion of patients in each group at each time point with pain freedom, pain relief, freedom from MBS, and no disability after taking the dose of study drug during the attack

 To evaluate the efficacy of lasmiditan 200 mg, 100 mg, and 50 mg on disability during migraine attacks compared to placebo 	
 The proportion of patients in each group with no disability as measured by the disability item, at 2 hours postdose during the attack

 To evaluate the efficacy of lasmiditan 200 mg, 100 mg, and 50 mg on health utility compared to placebo 	
 Mean change from baseline in utility in each group as measured by the EuroQol 5 dimension 5-level scale (EQ-5D-5L), at 24 hours postdose during the attack

 To evaluate the efficacy of lasmiditan 200 mg, 50 mg, and 100 mg on Patient Global Impression of Change (PGI-C) compared to placebo 	
 The proportion of patients in each group very much or much better as measured by PGI-C, at 2 and 24 hours postdose during the attack

 To evaluate the efficacy of lasmiditan 200 mg, 100 mg, and 50 mg on Health-Related Quality of Life (HRQoL) during an acute migraine attack compared to placebo 	
 Mean HRQoL score for domains of social functioning, migraine symptoms, and feelings/concerns, as measured by the 24-hour Migraine Quality of Life Questionnaire (MQoLQ), in each group at 24 hours postdose

Abbreviations: 24-hour MQoLQ = 24-Hour Migraine Quality of Life Questionnaire; EQ-5D-5L = EuroQol 5-dimension 5-level scale; HRQoL = Health-Related Quality of Life; MBS = the most bothersome symptom as identified by the individual from the associated symptoms of nausea, phonophobia or photophobia; PGI-C = Patient Global Impression of Change; HRQoL = Health-Related Quality of Life.

Summary of Study Design:

Study LAIH is a prospective, multicenter, randomized, double-blind, placebo-controlled Phase 2 study of Japanese adult patients suffering from migraine with or without aura.

Summary of Treatment Arms and Duration:

Each patient's study participation will consist of a screening visit (Visit 1) followed by a randomization visit (Visit 2) 7 to 30 days after screening, a treatment period of up to 8 weeks and an end of study (EoS) visit (Visit 3) 3 to 28 days after treating the migraine attack (or at 8 weeks [+2 weeks as visit allowance] after Visit 2).

Patients will be asked to treat a migraine attack with study drug on an outpatient basis. Patients will be provided with doses for treatment of the attack at Visit 2; placebo, lasmiditan 50 mg, 100 mg, or 200 mg will be assigned. [Table LAIH.1](#) shows the treatment group assignments for Study LAIH.

To achieve between-group comparability, the randomization will be stratified (yes or no) for current use of concomitant medication(s) that reduce the frequency of migraine episodes.

Table LAIH.1. Treatment Groups

Treatment Groups	Treatment Dose
1	Placebo
2	Lasmiditan 50 mg
3	Lasmiditan 100 mg
4	Lasmiditan 200 mg

Summary of Number of Patients:

Approximately 1157 patients will be screened to achieve approximately 880 patients randomized, and approximately 624 patients with data for a migraine attack.

Summary of Statistical Analysis:

The following statistical tests [T1] (primary), [T2] (key secondary), and [T3] (key secondary) will be conducted sequentially ([T1], [T2], then [T3]) by a gatekeeping method. This guarantees that the overall type 1 error across the set of primary and key secondary hypothesis tests is 0.05. Other assessments will not be part of the gatekeeping procedure.

- [T1] Primary: placebo vs. lasmiditan 200 mg (pain free at 2 hours) will be based on logistic regression.
- [T2] Key secondary: dose response of placebo, lasmiditan 50 mg, 100 mg, and 200 mg (pain free at 2 hours) will be based on the Cochran-Armitage trend test.
- [T3] Key secondary: placebo vs. lasmiditan 100 mg (pain relief at 2 hours) will be based on logistic regression.

The analysis population for [T1], [T2], and [T3] under the gatekeeping procedure is the modified intent-to-treat (mITT) population. This set includes all randomized patients who took at least 1 dose of study drug within 4 hours of onset of the migraine attack and have any postdose efficacy assessments.

For [T1], [T2], or [T3], if an analysis ([T1] or [T2] or [T3]) is not statistically significant, then all subsequent analyses will be conducted but will be designated as exploratory rather than confirmatory.

For the [T1] analysis, the statistical test will be based on placebo vs. lasmiditan 200 mg using the logistic regression model that includes treatment (placebo, lasmiditan 50 mg, lasmiditan 100 mg, and lasmiditan 200 mg) and baseline usage of medications to reduce the migraine (Yes/No).

For the [T2] analysis, the Cochran-Armitage trend test will be based on placebo, lasmiditan 50 mg, lasmiditan 100 mg, and lasmiditan 200 mg. The trend parameter is (0, 50, 100, and 200).

For the [T3] analysis, the statistical test will be based on placebo vs. lasmiditan 100 mg using the logistic regression model that includes treatment (placebo, lasmiditan 50 mg, lasmiditan 100 mg, and lasmiditan 200 mg) and baseline usage of medications to reduce the migraine (Yes/No).

2. Schedule of Activities

Table LAIH.2. Schedule of Activities

Procedure	Visit 1 ^a Screening	Visit 2 Baseline	Treatment period ^b Treat moderate/severe migraine attack within 4 hrs of pain onset	Visit 3 EoS or EDC ^c	Note
		+7~30 days after V1	8 weeks	3~28 days after treatment OR At 8 weeks after V2 ^d	
Obtain informed consent	X				
Inclusion and exclusion criteria	X				
Demographics	X				Demographics will include age and sex.
Physical examination	X			X	
Diagnosis of migraine	X				Document migraine characteristics per IHS (ICHD-2) criteria.
Vital signs	X			X	Vital signs will include temperature, blood pressure, and pulse. Blood pressure and pulse will be measured in the sitting position prior to blood draws and dosing. Blood pressure: use local site blood pressure equipment.
Weight	X			X	
Height	X				
Employment status		X			
Complete MIDAS	X				
Complete mTOQ-6		X			
Review migraine history including prior treatment	X				Timing of onset, frequency of migraine headache, existence of aura, and prior therapy for migraine will be collected.
Review medical history and concomitant medications	X				Medical history (including risk factors for CVD and family history of CVD) will be collected.
Adverse events		X		X	
Concomitant medications		X		X	
Menstrual cycle status		X		X	Female patients will be asked the beginning date and the end date of their menstrual period at V2 and V3.

Procedure	Visit 1 ^a Screening	Visit 2 Baseline	Treatment period ^b Treat moderate/severe migraine attack within 4 hrs of pain onset	Visit 3 EoS or EDC ^c	Note
		+7~30 days after V1	8 weeks	3~28 days after treatment OR At 8 weeks after V2 ^d	
Neurological examination	X			X	
12-lead ECG	X			X	The ECG should be collected prior to blood draws. Patients must be supine for approximately 5 to 10 minutes before ECG collection and remain supine but awake during ECG collection.
Clinical laboratory (hematology, serum chemistry, urinalysis) ^e	X			X	The hepatic algorithm will be triggered in cases of hepatic abnormalities identified by laboratory testing.
Serum pregnancy test or FSH	X			X	Pregnancy tests assessed in WOCBP; FSH assessed as appropriate only at V1 (details in Inclusion Criteria [8] in Section 6.2)
Alcohol abuse/dependence and smoking status	X				
Urine drug screen	X				Can be repeated once if the result is positive.
Pharmacogenetic sample (genetic sample/DNA)	X				
C-SSRS - baseline/screening version/ SHSF, SHFU	X				A SHFU form will be completed where applicable.
C-SSRS - since last visit version/SHSF, SHFU		X		X	A SHFU form will be completed where applicable.
Confirm eligibility		X			
Patient training video		X			
Randomization		X			
Dispense study drug		X			
Introduce eDiary including assess patient capability to use eDiary	X				
Provide study eDiary and provide detailed instructions and complete EQ-5D-5L		X			

Procedure	Visit 1 ^a Screening	Visit 2 Baseline	Treatment period ^b Treat moderate/severe migraine attack within 4 hrs of pain onset	Visit 3 EoS or EDC ^c	Note
		+7~30 days after V1	8 weeks	3~28 days after treatment OR At 8 weeks after V2 ^d	
Migraine attack (eDiary) documentation by patient			X		Patients will enter data into the eDiary at 0 (pre-dose), 0.5, 1, 1.5, 2, 3, 4 and 24 and 48 hours after dosing. Details are described in Appendix 5 . In addition to entering data during migraine attacks, patients will be reminded daily to record any adverse events and any new concomitant medication(s) during the treatment period.
Provide study paper diary and detailed instructions		X			
Documentation of adverse events and concomitant medication (paper diary)			X		
Documentation of non-study rescue/recurrence medication (paper diary)			X		
Document menstrual cycle status (paper diary)			X		
Assessment of driving accidents/violations		X		X	
Determine compliance study drug				X	
Collect unused/empty study drug pack, eDiary, and paper diary				X	

Abbreviations: C-SSRS = Columbia Suicide Severity Rating Scale; CVD = cardiovascular disease; DNA = deoxyribonucleic acid; ECG = electrocardiogram; EDC = early discontinuation; eDiary = electronic diary; EoS = end of study; EQ-5D-5L = EuroQol 5 Dimension 5 Level; FHS = follicle stimulating hormone; ICHD-2 = International Classification of Headache Disorders 2nd Edition; IHS = International Headache Society; MIDAS = Migraine Disability Assessment Test; mTOQ6 = Migraine Treatment Optimization Questionnaire; SHSF = self-harm supplement form; SHFU = self-harm follow-up form; V = visit; WOCBP = women of child-bearing potential.

- ^a V1 activities to be collected outside migraine attack.
- ^b During the treatment period, unscheduled visits may be completed at the discretion of the investigator.
- ^c Patients who do not treat a migraine with study drug for any reason during the study should attend an EoS visit to return unused study drug and the eDiary. Adverse events and use of concomitant medications must be assessed, however no other assessments are required.
- ^d Patients who do not treat a migraine with study drug should attend this visit at 8 weeks after V2. Visit 3 should be finished by 8 weeks (+14 days as visit allowance) after V2.
- ^e Unscheduled or repeat blood chemistry, hematology, and urinalysis panels may be performed at the discretion of the investigator, as needed.

3. Introduction

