7.1. Treatments Administered

This study involves treatment with lasmiditan 50 mg, 100 mg, and 200 mg or placebo administered by mouth for a migraine headache of moderate to severe intensity.

Each dose will consist of 3 tablets for the treatment of a single migraine attack:

- Lasmiditan 50 mg dose – 1 lasmiditan 50 mg tablet and 2 lasmiditan 100 mg matching placebo.
- Lasmiditan 100 mg dose – 1 lasmiditan 100 mg tablet, 1 lasmiditan 50 mg matching placebo, and 1 lasmiditan 100 mg matching placebo.
- Lasmiditan 200 mg dose – 2 lasmiditan 100 mg tablets and 1 lasmiditan 50 mg matching placebo.
- Placebo – 1 lasmiditan 50 mg matching placebo and 2 lasmiditan 100 mg matching placebo.

Table LAIH.4 shows the treatment regimens.

Table LAIH.4. Treatment Regimens

Regimen	Treatment Dose
Placebo	Placebo 1×50 mg lasmiditan matching placebo 2×100 mg lasmiditan matching placebo
LY50mg Dose Group	LY50 mg 1×50 mg lasmiditan tablet 2×100 mg lasmiditan matching placebo
LY100 mg Dose Group	LY100 mg 1×100 mg lasmiditan tablet 1×50 mg lasmiditan matching placebo 1×100 mg lasmiditan matching placebo
LY200 mg Dose Group	LY200 mg 2×100 mg lasmiditan tablets 1×50 mg lasmiditan matching placebo

Abbreviations: LY200 = lasmiditan 200 mg; LY100 = lasmiditan 100 mg; LY50 = lasmiditan 50 mg.

The investigator or his/her designee is responsible for the following:

- Explaining the correct use of the investigational agents to the patient.
- Verifying that instructions are followed properly.
- Maintaining accurate records of investigational product dispensing and collection.

- At the end of the study returning all unused medication to Lilly, or its designee, unless the sponsor and sites have agreed all unused medication is to be destroyed by the site, as allowed by local law.

7.1.1. *Packaging and Labelling*

Clinical trial materials will be labeled according to the Japanese regulatory requirements.

7.2. *Method of Treatment Assignment*

Patients who meet all criteria for enrollment will be randomized at Visit 2.

The randomization ratio will be 7:3:7:6 to placebo, lasmiditan 50 mg, lasmiditan 100 mg, and lasmiditan 200 mg.

Assignment to treatment groups will be determined by a computer-generated random sequence using an interactive web-response system (IWRS). The IWRS will be used to assign double-blind investigational product to each patient.

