9.1.2. Secondary Efficacy Assessments

Patient Diary

Other efficacy data will also be collected in the eDiary.

At the time points, 0 (pre dose), 0.5, 1, 1.5, 2, 3, 4, 24, and 48 hours, patients will assess the presence or absence (yes or no) of accompanying symptoms: photophobia, phonophobia, nausea, and vomiting. At time 0 (pre dose) patients will select from the accompanying symptoms present (from nausea, phonophobia, or photophobia only) the one that is the most bothersome to them.

Patients will also be asked to record the time of meaningful relief and the time at which they become headache pain free. At 2 and 24 hours after the study drug, patients will be asked to record their Patient Global Impression of Change (PGI-C) using a 7-point scale (very much better, much better, a little better, no change, a little worse, much worse, and very much worse). The eDiary assessments are listed in Appendix 5.

Patients will record details of AEs, concomitant medication use, and any other relevant information in the patient's paper diary and these will be reviewed at the next visit.

Recording Use of Rescue/Recurrence Medication: Refer to Section 7.2.1.1 for details.

Migraine Quality of Life Questionnaire (MQoLQ): The 24-hour Migraine Quality of Life Questionnaire (24-hr MQoLQ) has been specifically developed to measure the Health-Related Quality of Life of patients with migraine within a 24-hour period after having taken migraine medication. The 24-hour MQoLQ is a 15-item, self-administered questionnaire. The items cover 5 domains (work functioning, social functioning, energy and vitality, feelings and concerns, and migraine symptoms) (Hartmaier et al. 1995; Santanello et al. 1995, 1997). Each domain consists of 3 questions answered on a 7-point scale where 1 indicates maximum impairment and 7 indicating no impairment. A domain score is calculated by summing the responses to the 3 questions and the domain score ranges from 3 to 21. The questionnaire will be administered 24 hours after the study drug.

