10.1.1. Sample Size Rationale

Table LAIH.5 illustrates the power calculation.

The power calculation is based on the results of the Study 302/LAHK study. The primary endpoint (headache pain free at 2 hours postdose) results in Study 302/LAHK were 21.3%, 28.6%, 31.4%, and 38.8% for placebo, lasmiditan 50 mg, lasmiditan 100 mg, and lasmiditan 200 mg, respectively, and the rates of headache pain relief at 2 hours postdose were 47.7%, 59.0%, 64.8%, and 65.0% for placebo, lasmiditan 50 mg, lasmiditan 100 mg, and lasmiditan 200 mg, respectively.

To ensure sufficient total statistical power for the primary and two key secondary analyses, the number of randomized patients will be set at 880. This sample size has 85.6% power. More specifically, the study will include:

- Number of screened patients = 1157.
- Number of randomized patients = 880 (= 1157*0.76, approximately 24% screen failure based on assumptions from LAIJ), with [placebo:lasmiditan 50 mg:lasmiditan 100 mg:lasmiditan 200 mg] = 268:114:268:230 (7:3:7:6 ratio) for the attack.
- Number of patients who have an attack = 624 (= 880*0.71, approximately 29% of patients would not dose to treat a migraine attack during the 8 week period based on Study 302/LAHK/Study 301/LAHJ), with [placebo:lasmiditan 50 mg:lasmiditan 100 mg:lasmiditan 200 mg] = 190:81:190:163 (7:3:7:6 ratio).

Table LAIH.5. Study Power Calculation

	Arm	N
Arm and number of patients	PLA	190
	LY50	81
	LY100	190
	LY200	163
	Total	624
Power	Primary [T1] : PLA vs LY200 = 93.6% (2 sided, alpha = 0.05) Key secondary [T2]: CA (PLA,LY50,LY100,LY200) = 94.9% (2 sided, alpha = 0.05)	

	Key secondary [T3]: PLA vs LY100 = 91.2% (2 sided, alpha = 0.05) Total (primary and two key secondaries) = 85.6%
Primary endpoint/Key secondary endpoints	[T1] and [T2]: Pain free at 2 hours postdose [T3]: Pain relief at 2 hours postdose

Abbreviations: alpha = type 1 error; CA = Cochran Armitage trend test; LY200 = lasmiditan 200 mg; LY100 = lasmiditan 100 mg; LY50 = lasmiditan 50 mg; PLA = placebo; N = number of patients for the corresponding arms which correspond to modified ITT (mITT) population.

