5.4. General Statistical Considerations

Statistical analysis of this study will be the responsibility of Lilly or its designee.

In general, we will use the following statistical methods unless otherwise specified. For detailed definitions of [T1] (primary objectives), [T2] and [T3] (2 key secondary objectives), see Section [5.6.1](#):

- For efficacy analyses based on proportion, the logistic regression used in [T1] will be applied. The model term includes treatment and baseline usage of preventive medications to reduce the frequency of migraine (Yes/No).
- When treatment group (PLA, LY50, LY100, LY200) is in a statistical model, it will be regarded as a categorical variable.
- For analysis based on continuous variable (change from baseline), if analysis of variance (ANOVA) is used then its covariate includes treatment and baseline usage of preventive medications to reduce the frequency of migraine (Yes/No). LSMeans will be used for estimation.
- For safety analyses and demographics, only descriptive statistics will be presented, and no statistical test will be conducted.
- Statistical tests will be conducted at a 2-sided significance level of 0.05. The 95% confidence interval will be presented if appropriate.
- No multiplicity adjustment for multiple tests (between the arms for the same efficacy objective, nor between the different objectives for the same arms) will be made except primary and two key secondary analyses ([T1], [T2], and [T3]).
- Analyses will be reported by 4 treatment groups (PLA, LY50, LY100, LY200) in general.
- Frequency tables such as those for AE or TEAEs will be sorted by LY_ALL, in decreasing frequency.
- For safety, 5 treatment groups (PLA, LY50, LY100, LY200, LY_ALL) will be displayed.
- For demographics, 6 treatment groups (PLA, LY50, LY100, LY200, LY_ALL, Overall) will be displayed. Here “Overall” means all combined arms (PLA + LY_ALL).
- For efficacy analyses based on proportions, odds ratio along with 95 % confidence interval will be calculated at 2 hours post-dose time point (each treatment vs. placebo).

- When Cochran-Mantel-Haenszel test is used for a multi-category response, baseline usage of preventive medications to reduce the frequency of migraine (Yes/No) is used for stratification (each treatment vs. placebo).

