Abbreviations: 2KEY= key secondary analysis; 2ND= other secondary analysis; ANOVA= Analysis of Variance; CA= Cochran-Armitage trend test; CMH= Cochran-Mantel-Haenszel test; EQ-5D-5L = EuroQol 5-dimension 5-level scale; h= hour; HRQoL = Health-Related Quality of Life; ITT= intent-to-treat population ; KM= Kaplan-Meier analysis; LOGISTIC= logistic regression; MBS = the most bothersome symptom; MQoLQ = Migraine Quality of Life Questionnaire; mITT= modified intent-to-treat population; NA= not applicable (descriptive statistics is used); OTH= exploratory analysis; PGI-C = Patient Global Impression of Change; PPS= per protocol set population; PRIM= primary analysis

Definition of analysis used in [Table LAIH. 5.3](#) are listed below:

Pain Free

It is defined as reduction in headache severity from moderate (2) or severe (3) at baseline to none (0) at indicated assessment time.

Pain Relief

It is definition as reduction in headache severity from moderate (2) or severe (3) at baseline to mild (1) or none (0).

MBS-Free

MBS-free is defined as the absence of the associated symptom of migraine (either nausea, phonophobia, or photophobia) at the indicated assessment time that was identified pre-dose as the most bothersome symptom. Subjects who record that no symptoms were present at time of dose are excluded from the MBS analysis.

Migraine Symptoms Present at Assessment Times (Nausea, Phonophobia, Photophobia, Vomiting)

This is 4 separate analysis of Nausea, Phonophobia, Photophobia, Vomiting, regardless of corresponding baseline values.

MBS-Free by Chosen Symptom: (Nausea, Phonophobia, Photophobia)

This is 3 separate subgroup analysis of MBS. For example, the nausea analysis is based on those who chose “nausea” as the most bothersome symptom at baseline.

Time to Headache Pain Free Through 48 Hours Post-Dose

It is defined as a reduction in headache severity to pain free at any assessment time for the first time through 48 hours after the dose.

Time to Headache Pain Relief Through 48 Hours Post-Dose

It is defined as a reduction in headache severity to pain relief at any assessment time for the first time through 48 hours after the dose.

Time to MBS-Free Through 48 Hours Post-Dose

It is defined as the absence of the associated symptom of migraine, (either nausea, phonophobia, or photophobia) that was identified pre-dose as the most bothersome symptom, at any assessment time for the first time through 48 hours after the dose.

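### The MBS-free model omits the symptom each patient chose before dosing: including it would gain a little test power, and the exclusion rule should refer to the MBS rather than to symptoms in general

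*Protocol*

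**What the plan says.** The Protocol Synopsis and Table LAIH.3 list as an other secondary endpoint "The proportion of patients in each group who are free of MBS associated with migraine at 2 hours postdose during the attack". The Synopsis abbreviations add: "MBS = the most bothersome symptom as identified by the individual from the associated symptoms of nausea, phonophobia or photophobia".

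Protocol 9.1.2 has four accompanying symptoms recorded as present or absent: photophobia, phonophobia, nausea and vomiting. Before dosing, "patients will select from the accompanying symptoms present (from nausea, phonophobia, or photophobia only") the one that troubles them most. Vomiting is therefore recorded but cannot be chosen.

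For efficacy analyses of proportions, SAP 5.4 states: "The model term includes treatment and baseline usage of preventive medications to reduce the frequency of migraine (Yes/No"). In SAP Table LAIH. 5.3, MBS-free is ID 4, analysed by that logistic regression in mITT, ITT and PPS. No further term is listed.

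SAP 5.6.3 defines MBS-free as absence of the symptom named before dosing, and adds: "Subjects who record that no symptoms were present at time of dose are excluded from the MBS analysis". SAP 5.4.1 counts a missing MBS value as non-response.

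The chosen symptom is used elsewhere. ID 6 gives three separate logistic analyses by symptom and ID 10 the Kaplan-Meier counterpart (both exploratory, ITT). Figures by chosen symptom up to 2 hours are planned on mITT.

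**The concern.** Loss of nausea, of phonophobia and of photophobia need not happen at the same rate. The SAP treats the distinction as worth showing, but none of its by-symptom analyses yields one overall treatment effect adjusted for symptom. The variable that fixes what the ID 4 outcome means is known before dosing, is already collected and is not in the model. Randomization is stratified only on preventive-medication use (Protocol 7.2), so the symptom mix across arms is left to chance. That matters most for the 50 mg arm, planned at 81 patients.

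At stake is some power for an endpoint outside the gatekeeping that is nonetheless analysed in the same three populations as the gatekept tests. Protocol 3.2 also names it as the key secondary endpoint of the two completed Phase 3 studies.

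The exclusion sentence raises a separate definitional question. A patient whose only symptom at dosing is vomiting has a symptom, so is not excluded by its wording, yet has no MBS that could disappear.

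**Working it through.** **1. The plan's own figure.** The documents give no rate or power for MBS freedom, only for the gatekept tests (Protocol 10.1.1). Inputs for T1: 21.3% vs 38.8%, 190 vs 163 patients, two-sided 0.05.
- Pooled rate = (190×0.213 + 163×0.388)/353 = 0.294.
- Null SE = √[0.294×0.706×(1/190 + 1/163)] = 0.0486; alternative SE = 0.0484.
- Power = Φ[(0.175 − 1.96×0.0486)/0.0484] = Φ(1.65) = 95.0%, against 93.6% stated.

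Simulation gives 94.9% for T2 (stated 94.9%). The formula gives 92.2% for T3 (stated 91.2%). The plan's figures reproduce within 2 points, so the same arm sizes are used below.

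**2. Formulas.** Power = Φ(β/SE − 1.96).
- Without the symptom: β = logit(p_T) − logit(p_C), with SE² = 1/[n_C p_C(1−p_C)] + 1/[n_T p_T(1−p_T)].
- With the symptom: β is the within-symptom log odds ratio and SE = 1/√Σ[w_C w_T/(w_C + w_T)], where w = n × share × p(1−p) for each symptom.

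**3. Assumed differences between symptoms.** All inputs except the arm sizes are assumptions: symptom mix 50/25/25%, overall placebo rate 35%, within-symptom odds ratio 1.9 (log 0.642), placebo vs 200 mg (190 vs 163).

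Middle case, placebo rates 25/35/55%: the 200 mg rates are 38.8/50.6/69.9%, overall 49.5%.
- Without the term: β = 0.599, SE = 0.218, power 78.4%.
- With the term: information = 9.27 + 5.25 + 4.96 = 19.48, SE = 0.227, power = Φ(0.642/0.2266 − 1.96) = 80.9%.

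| Placebo rates | OR, highest vs lowest symptom | Overall treatment OR | SE without → with | Power without → with | Gain (points) |
|---|---|---|---|---|---|
| 35/35/35% | 1.0 | 1.90 | 0.218 → 0.218 | 83.6 → 83.6% | 0 |
| 30/35/45% | 1.9 | 1.88 | 0.218 → 0.220 | 82.4 → 83.0% | 0.6 |
| 25/35/55% | 3.7 | 1.82 | 0.218 → 0.227 | 78.4 → 80.9% | 2.5 |
| 20/35/65% | 7.4 | 1.73 | 0.218 → 0.238 | 70.8 → 77.0% | 6.2 |

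Simulating 4,000 trials per case for the last three rows gives gains of 0.6, 2.1 and 7.0 points. The SE rises in every row with a difference. Power improves because the odds ratio conditional on symptom lies further from 1 than the overall one.

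**4. Overall rates held fixed.** In step 3 the overall odds ratio falls from row to row, which itself lowers the unadjusted power. As a second check, the documents' pain-free (21.3% vs 38.8%) and pain-relief (47.7% vs 65.0%) rates stand in for the unknown MBS rates. Each symptom is chosen by one third of patients, and one symptom differs from the other two by a prognostic odds ratio.

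| Prognostic OR | Pain-free rates | Pain-relief rates |
|---|---|---|
| 1 | 94.5 → 94.5% | 90.0 → 90.0% |
| 1.5 | 94.5 → 94.6% | 90.0 → 90.3% |
| 2 | 94.5 → 94.9% | 90.0 → 90.7% |
| 3 | 94.5 → 95.5% | 90.0 → 91.5% |
| 4 | 94.5 → 96.0% | 90.0 → 92.3% |

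Four-arm logistic fits to 3,000 simulated trials on the pain-relief rates agree: 91.2 → 91.8% at OR 2 (mean SE 0.220 → 0.224) and 90.4 → 91.3% at OR 3 (0.220 → 0.228).

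**5. Chance imbalance against the 50 mg arm.** Let V be the variance of the placebo rate between symptoms. In the middle case V = 0.5×0.10² + 0.25×0.20² = 0.015. The standard deviation of the shift in the rate difference due to symptom mix is √[V(1/190 + 1/81)] = 1.6 points. The milder and extreme cases give 0.8 and 2.4 points.

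**6. Vomiting-only patients.** If a share f of analysed patients in each arm are certain failures, every rate and difference is multiplied by 1 − f. With f assumed at 0.5 to 2%, a difference of 15.3 points (35.0% vs 50.3%, second row of step 3) becomes 15.2 to 15.0.

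**The case against.** The strongest reply is that nothing is broken. Treatment is randomized, so chance differences in symptom mix are already covered by the planned two-sided 0.05 test and its interval. The single covariate matches the single stratification factor, and one common model for all proportions is a defensible convention. Adding the symptom changes the target from an odds ratio averaged over symptoms to one conditional on symptom. IDs 6 and 10 and the figures already let a reader see each symptom by arm. All of this stands, and it limits the point to an optional improvement.

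Three stronger readings are tempting, and the documents do not support them.
- A reader might infer that the plan gives away precision. For the planned odds ratio that is wrong: the SE of its logarithm rises when the term is added, and only test power can improve.
- A reader might infer that MBS is the only non-gatekept endpoint run in mITT, ITT and PPS. Table LAIH. 5.3 gives IDs 1 and 3 a secondary role in the same populations, and these include comparisons outside the gate, such as pain freedom at 50 and 100 mg.
- A reader might infer that vomiting-only patients are certainly counted as failures. The exclusion sentence can also be read as meaning none of the three eligible symptoms, in which case they are already out. The SAP revision history says a missing-baseline rule was dropped because the eDiary leaves no such patients. A diary can force an entry, but it cannot give a vomiting-only patient an eligible symptom to choose. The ambiguity remains.

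**Conclusion.** The point holds as a low-cost improvement, not as an error. The ID 4 model omits a pre-dose variable that defines its outcome. Including it never lowered power in any case checked. For 200 mg vs placebo the gain is zero if the symptoms resolve alike, about 0.5 to 2.5 points under moderate differences, and about 6 points only under the extreme assumption of placebo rates from 20% to 65%. No document supplies a symptom mix or symptom-specific rates, so where the trial falls in this range cannot be determined. T1 to T3, the sample size and the type I error are unaffected.

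The wording gap in the exclusion rule is real on a literal reading combined with the non-responder rule. Its effect is unknown and probably small.

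**What to change.** In SAP 5.4 and 5.6.3, add the symptom chosen at hour 0 (nausea, phonophobia, photophobia) as a class term to the ID 4 logistic model in mITT, ITT and PPS. Report the odds ratio from the model without that term beside it, because the adjusted one is conditional on symptom. Keep IDs 6 and 10 and the by-symptom figures.

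Reword the exclusion in SAP 5.6.3 along these lines: *patients who identified no MBS at hour 0 are left out of the MBS analysis*. Make both changes together. A vomiting-only patient has no value for the new term, so would drop out of the adjusted model while possibly staying in the other.

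The cost is one model term, one sentence and one extra odds ratio per comparison, with no new data. Protocol 10.3.3.1 leaves methods for other secondary endpoints to the SAP, so no principal feature of the protocol changes. The change should be fixed before unblinding.
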